Фонд за науку
Републике Србије

Utility of plasma drug level monitoring and *CYP2C19* genotyping in dose personalization of escitalopram therapy

PsyCise_E

Principal Investigator: **Asst. [name] PhD**

Department of Physiology, Faculty of Pharmacy, University of Belgrade, Serbia

Document Date: 12th January 2022

Clinical trial protocol

Test groups:

PsyCise trial is designed to quantify changes in clinical outcomes in participants treated for depression using personalized antidepressant dosing regimen, based on therapeutic drug monitoring (TDM) and CYP2C19 genotyping; as compared to the standard, “one size fits all” dosing. In order to reach this goal, we have defined two test groups based on the TDM findings. Namely, all participants who enter the trial (Visit 0) will begin taking standard escitalopram dose of 10 mg/day for two weeks when their blood samples will be taken for the purpose of TDM, and based on their steady state escitalopram concentrations they will be allocated to one of two groups at week 4 of the trial (visit 1):

- 1) “Standard dose” group: Participants will be allocated to this group if their TDM results at week 2 show their steady state escitalopram plasma concentrations were inside “therapeutic window” (25-50 ng/ml). For these participants, initial standard escitalopram dose of 10 mg/day is estimated to be optimal so they will continue to receive the same dose until the end of the trial at week 8 (visit 2).
- 2) “Adjusted dose” group: If TDM results at week 2 suggest that participant taking standard dose is underdosed or overdosed, given participant is allocated to this group. New, personalized dosing regimen will be produced for this participants based on steady state escitalopram plasma concentrations measured at week 2, and they will receive personalized escitalopram dose from week 4 (visit 1) until the end of the trial at week 8 (visit 2).

Course of the trial:

Week 0

Initial Visit (Visit 0 – V0)

- Participant will be enrolled at this point if inclusion criteria are met.
- Escitalopram monotherapy for Major Depressive Disorder in previously untreated patient will be initiated at standard dose of 10 mg/day.
- Outcomes measured:
 1. General and socio-demographic information
 2. Clinical questionnaires
 3. Anthropometric measurements
 4. Cardiological assessment
 5. Serum samples for biochemical analyses
 6. Buffy coat samples for DNA extraction and *CYP2C19* genotyping*

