- Clinician who usually monitors given patient is unaware of the group patient is allocated to, or the dose prescribed to a patient at Visit 1.
- Outcomes measured:
 1. Clinical questionnaires
 2. Anthropometric measurements
 3. Cardiological assessment
 4. Serum samples for biochemical analyses
 5. Plasma samples to reconfirm TDM findings in V_k

Week 6

Visit 2 (V2) – *Identical to the standard protocol*

- Final visit of the trial and the end of the follow-up.
- Outcomes measured:
 1. Clinical questionnaires
 2. Anthropometric measurements
 3. Cardiological assessment
 4. Serum samples for biochemical analyses
 5. Plasma samples to reconfirm TDM findings in V_k and V1 for Standard dosing group, and to determine whether personalized dose is optimal for the patients in Personalized dosing group.

Hypotheses:

- 1) More than one quarter of participants will be overdosed or underdosed under standard escitalopram dosing regimen (10 mg/day), as determined by TDM data 2 weeks after the beginning of the therapy.
- 2) Participants with escitalopram steady state plasma concentration outside the therapeutic window (“Adjusted dose” group) will experience reduced efficacy and more severe side effects of escitalopram therapy before dose personalization (at V1) compared to the participants with escitalopram levels within therapeutic window (“Standard dose” group) at standard dosing.
- 3) Participants with escitalopram steady state plasma concentration outside the therapeutic window (“Adjusted dose” group) will show improved efficacy and less severe side effects of escitalopram therapy after dose personalization (at V2) as compared to before (at V1), and will reach clinical outcomes comparable to the “Standard dose” group (at V2).

- 4) Decisions on whether to use personalized or standard dosing, and how to adjust personalized dose based on TDM data could have been determined before the beginning of the treatment using predictive model which, besides other predictors also includes *CYP2C19* genotyping data.

Statistical Analysis Plan

Primary outcomes:

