To assess the efficacy of the escitalopram therapy under different dosing regimens we will use 21-item Hamilton rating scale for depression (HAM-D). Depression severity score will be measured at baseline (V0), at week 4 (V1) and week 8 (V2) after the beginning of the treatment. Since there is the need to compare depression severity scores between two test groups as well as between the visits V1 and V2, mixed analysis of covariance (Mixed ANCOVA) will be used if all assumptions associated with ANCOVA are met. Variables will be assigned as follows:

1. Dependent variable: Depression severity score measured by HAM-D scale
2. Independent variable - Fixed factor: Test group (Personalized vs Standard dosing)
3. Independent variable - Repeated measurements: Visit (Visit 1 vs Visit 2)
4. Covariates: Baseline HAM-D score (V0), Childhood trauma questionnaire score at V0, Age, Sex (Male=0, Female=1), Smoking status (0=Non-smoker, 1=Smoker), Alcohol consumption (0=No, 1=Yes), Metabolic syndrome diagnosed using siMS score [Soldatović 2016] (0=No, Yes)

Positive outcome: interaction between group and visit is significant ($\alpha=0.05$)

Besides using absolute HAM-D scores, we will also compare relative changes in HAM-D scores between V1 and V2 visits as another way to express the potential differences in therapy efficacy between the two test groups. If all needed assumptions are met, statistical test used will be analysis of covariance (ANCOVA) with variables assigned as follows:

1. Dependent variable: Relative change in HAM-D score between visits V1 and V2 calculated by formula:

$$\frac{HAMD_{V1} - HAMD_{V2}}{HAMD_{V1}}$$

2. Independent variable: Test group (Personalized dosing vs Standard dosing)
3. Covariables: Baseline HAM-D score (V0), Childhood trauma questionnaire score at V0, Age, Sex (Male=0, Female=1), Smoking status (0=Non-smoker, 1=Smoker), Alcohol consumption (0=No, 1=Yes), Metabolic syndrome (0=No, Yes)

Positive outcome: Test group is a significant factor ($\alpha=0.05$)

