2. Covariables: Test group (Personalized vs Standard dosing), Age, Sex (Male=0, Female=1), Smoking status (0=Non-smoker, 1=Smoker), Alcohol consumption (0=No, 1=Yes), Coffee consumption (0=No, 1=Yes), Use of psychoactive substances (0=No, 1=Yes), Metabolic syndrome (0=No, 1=Yes), Creatinine clearance, AST/ALT ratio.

Positive outcome: Test group is a significant factor ($\alpha=0.05$)

Secondary outcomes:

Retrospective TDM data on 2087 patients taking escitalopram [Jukić 2018] suggests that, in the clinical setting, about 40% of patients are expected to have their plasma escitalopram concentrations under the lower limit of the therapeutic window (25 ng/ml), and for about 10% of patients we expect to have plasma escitalopram levels above the upper limit of the therapeutic window (50 ng/ml). One of our aims is to try to confirm these findings using prospective study design which allows for the better control of the confounding factors compared to the retrospective data. Number of the patients with plasma escitalopram levels outside the therapeutic window under standard dosing regimen (10 mg/day) will be assessed using TDM data at Mid-Visit (VK), 2 weeks after the beginning of the therapy.

Big disadvantage of TDM guided establishment of the optimal drug exposure in the given patient is that it takes 4 weeks to personalize escitalopram dose and 2 more weeks to achieve optimal steady state drug concentrations. Alternative approach would be to build model that could predict optimal dose for every patient even before the initiation of the treatment. This model would have to include patient data on factors that could impact escitalopram exposure such as body weight, liver and kidney functions and genotype for the *CYP2C19* gene which is responsible for the interindividual variability in the rate of escitalopram metabolism in liver [Jukić 2018]. After all participants have finished the trial we will retrospectively build model using data collected during the trial, and then validate our model comparing it to the TDM method of dose personalization. For this purpose, all patients will be genotyped for *CYP2C19* gene and divided into 4 groups based on the enzymatic capacity of CYP2C19 enzyme:

1. Poor metabolizer (PM): Carries *2/*2, *2/*3 or *3/*3 *CYP2C19* genotype. Almost absent CYP2C19 enzyme activity
2. Intermediate metabolizer (IM): Carries *1/*2 or *1/*3 *CYP2C19* genotype. Reduced CYP2C19 enzyme activity

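### HAM-D has two primary success rules at 0.05 that test different nulls; with V1 expected to differ between groups they can contradict each other, and either one can be claimed as positive

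*Combined protocol and SAP*

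**What the plan says.** All references are to the combined protocol and SAP.

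- **Statistical Analysis Plan, Primary outcomes.** The first HAM-D analysis is a mixed ANCOVA of absolute scores at V1 and V2. It is positive if the group-by-visit interaction is significant at 0.05. The second is an ANCOVA of the "Relative change in HAM-D score between visits V1 and V2 calculated by formula", with (V1−V2)/V1 as the formula. It has its own rule at 0.05: "Positive outcome: Test group is a significant factor". Neither rule states a direction.
- **Covariates of the second analysis.** The list begins "Covariables: Baseline HAM-D score (V0), Childhood trauma questionnaire score at V0, Age, Sex (Male=0, Female=1" and continues with smoking, alcohol and metabolic syndrome. HAM-D at V1 is not in it.
- **Test groups.** Participants are not randomised: "based on their steady state escitalopram concentrations they will be allocated to one of two groups at week 4 of the trial".
- **Hypotheses 2 and 3.** Participants outside the therapeutic window "will experience reduced efficacy and more severe side effects of escitalopram therapy before dose personalization (at V1"), and after dose adjustment should improve "and will reach clinical outcomes comparable to the" Standard dose group at V2.
- **Secondary outcomes.** The expected split is near 1:1, since "about 40% of patients are expected to have their plasma escitalopram concentrations under the lower limit of the therapeutic window" and about 10% are expected above the upper limit.

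The SAP does not say whether no effect means equal point change or equal percentage change, which HAM-D rule prevails if the two disagree, or what happens when V1 is 0.

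**The concern.** The denominator of the second outcome is an on-treatment score that the trial's own hypothesis expects to differ between the groups. Neither the design nor the model balances it. When V1 means differ and scores fall, equal point change and equal percentage change cannot both be true. The two analyses are presented as two expressions of one effect, but they ask different questions.

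Three things are at stake. A primary rule can be met when the other null is true. One rule can favour Adjusted while the other favours Standard, and both would count as positive. Having two routes to success also raises the overall error rate above 0.05 with no V1 gap at all.

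**Working it through.** **Inputs from the documents.** The formula, alpha 0.05 (taken as two-sided), the covariate list, non-random groups, a split near 1:1, and the expected direction of the V1 gap. The documents give no sample size, SD, V1 gap or power figure, so there is no planned figure to reproduce.

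**Arithmetic on group means** (V1 of 11 in Standard and 14 in Adjusted, assumed).

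- Equal 4-point fall: 4/11 = 36.4% and 4/14 = 28.6%. The ratio is 7.8 percentage points against Adjusted with no difference in points.
- Equal 30% fall: 0.3 × 11 = 3.3 and 0.3 × 14 = 4.2. The absolute change is 0.9 points in favour of Adjusted with no difference in percentage.
- Contradiction zone: if Standard falls 4, Adjusted matches it in percentage only at 14 × 4/11 = 5.1 points. A mean fall in Adjusted between 4 and 5.1 favours Adjusted in points and Standard in percentage.
- Power: with an extra 2.5 points, Adjusted falls 6.5/14 = 46.4%, which is 10.0 percentage points above Standard. From a V1 of 11, the same benefit would be 6.5/11 = 59.1%, or 22.7 above.

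**Simulation** (2,000–4,000 trials per scenario). Assumed: 75 per group; V0 mean 22, SD 4; V1 SD 6, correlation 0.4 with V0; V2-on-V1 slope 0.7 (in the equal-percentage rows, one minus the percentage fall), residual SD 4; integer scores floored at 0; patients with V1=0 dropped from the ratio. Models adjust for V0; the other covariates are left out. The absolute change adjusted for V0 stands in for the interaction, to which it is equivalent with two visits.

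Rejection rates with no true effect on the scale named:

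| Truth | Ratio rule | Absolute test | V0 denominator | V2 adjusted for V1 and V0 | Either planned rule |
|---|---|---|---|---|---|
| 11 vs 14, equal 4-point fall | 14% (nearly all favour Standard) | 5–6% | 5–6% | 25% (favour Standard) | 18–19% |
| 11 vs 14, equal 30% fall | 5% | 30% (favour Adjusted) | 30% | 5% | 32% |
| 11 vs 14, equal 36% fall | 5–6% | 37–39% | 36–39% | 5% | 39% |
| 11 vs 14, same V2-on-V1 line | 5% | 31% (favour Adjusted) | 30–31% | 5% | 33% |
| No V1 gap | 5% | 5–6% | 5–6% | 5% | 7–9% |

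If the two HAM-D tests were independent, the last cell would be 1 − 0.95² = 9.75%. Their correlation brings it to 7–9%.

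**Power** for a true extra 2.5 points, 11 vs 14. Equal-point setting: ratio 44–48%, absolute 94–95%. Same-line setting: ratio 82%. Equal-percentage setting: ratio 85–86%. With no gap (both 11): ratio 84–85%, absolute 86–87%.

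**V1=0.** At 11 vs 14 this affects about 4.0% of Standard and 1.2% of Adjusted, 2.6% overall. It is about 3.5% overall at 10 vs 14, and 4% if both means are 11. These patients, the best responders at V1, have no defined ratio, and they are unevenly spread.

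**Second set of assumptions** (V1 14 vs 17, SD 5, V0–V1 correlation 0.5, N=200 in total). Equal-point truth: ratio 24%. Equal-percentage truth: ratio 4–6%, absolute 35%. With a common V2-on-V1 line, the ratio rejects in 50%, 21%, 4%, 9% and 24% at slopes 0.3, 0.5, 0.7, 0.85 and 1.0. It favours Adjusted at low slopes and Standard at high ones, so the 5% in the same-line row above belongs to a slope near 0.7.

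**The case against.** A relative-change outcome naturally tests equal percentage change, and on that null the ratio rule holds its level at every V1 gap examined. A patient who falls 4 from 11 has had a larger relative change than one who falls 4 from 14. The equal-point scenario is also not neutral: with slope 0.7 and both means falling 4, an Adjusted patient ends 0.3 × 3 = 0.9 points worse than a Standard patient with the same V1. That is why V2 adjusted for V1 and V0 rejects in 25% there. The SAP introduces the ratio after the absolute test as an alternative expression, and uses ANCOVA only if its assumptions are met.

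Most of this stands, and it limits the point. A reader might infer that the V1 denominator simply reports differences that do not exist and loses power. The documents do not support that, because they never fix the null scale; on the percentage scale it is the absolute test that is inflated.

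A reader might also infer that dividing by V0 cures the problem. It does not. In these runs it behaves like the absolute change, rejecting in about 30% or more under an equal-percentage or common-line null. V0 is also not a uniform baseline: in the alternative course, participants enter after more than two weeks on escitalopram, so V0 is an on-treatment score.

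The objection does not answer the two separate success rules. Whatever the intent, the ratio stands under Primary outcomes with its own criterion, and a difference in either direction meets it.

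**Conclusion.** The point holds as one about hierarchy and consistency. The two HAM-D rules test different nulls, the trial's own hypothesis predicts the imbalance that separates them, and either can be called positive. That the nulls differ, that the rules have no direction and that V1=0 is not covered follow from the text alone.

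The sizes rest on assumed sample sizes, SDs, V1 gaps and slopes. At 11 vs 14 with 75 per group, the ratio rule is positive in about 14% under equal point change and about 5% under equal percentage change; the absolute test is at about 5–6% and 30% or more respectively. Success on either rule is about 7–9% with no gap, and 18–19% under equal point change with the gap. No denominator or covariate choice examined is safe under every null, and none removes confounding from non-random groups.

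**What to change.** In the SAP:

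1. Name the group-by-visit interaction on absolute HAM-D as the single primary HAM-D test. State that its null is equal point change from V1 to V2, and acknowledge that it can reject in favour of Adjusted if the groups instead improve by equal percentages.
2. Make the relative change supportive, with no success rule of its own.
3. Count as positive only a difference favouring the Adjusted group.
4. State in advance how V1=0 is handled in the ratio, and report the number of such patients by group. They remain in the primary test, where the score is defined.
5. Add a sensitivity analysis of V2 HAM-D adjusted for V1 and V0. Note that its validity also depends on the null (25% rejection under equal point change at 11 vs 14), and that it does not remove confounding.
6. Do not present a V0 denominator as a correction.

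The cost is SAP text only, since V0, V1 and V2 HAM-D are already collected. The downside is one fewer route to a positive primary result.

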Other primary outcome we will use to quantify changes in clinical outcomes between test groups will be severity of the treatment side effects measured using clinician reported UKU (*Udvalg for Kliniske Undersogelser*) side effect rating scale. UKU scale rates 48 potential adverse reactions with intensity score ranging from 0 to 3 where score 3 signifies maximal intensity and score 0 signifies absence of the adverse reaction. Adverse drug reaction intensity scores for all 48 adverse reactions monitored with UKU scale will be measured at weeks 4 (V1) and 8 (V2) after the initiation of the escitalopram therapy. Due to large number of comparisons, significance measures will be adjusted using False Discovery Rate (FDR) correction. Absolute values of all 48 Adverse reaction scores will be compared between test groups and between two time points using mixed model analysis of covariance (Mixed ANCOVA) where variables will be assigned as follows:

1. Dependent variable: Adverse drug reaction score for the given adverse reaction measured by UKU scale
2. Independent variable - Fixed factor: Test group (Personalized vs Standard dosing)
3. Independent variable - Repeated measurements: Visit (Visit 1 vs Visit 2)
4. Covariables: Age, Sex (Male=0, Female=1), Smoking status (0=Non-smoker, 1=Smoker), Alcohol consumption (0=No, 1=Yes), Coffee consumption (0=No, 1=Yes), Use of psychoactive substances (0=No, 1=Yes), Metabolic syndrome (0=No, 1=Yes), Creatinine clearance, AST/ALT ratio.

Positive outcome: interaction between group and visit is significant ($\alpha=0.05$)

Alternatively, proportions of patients with intensity score greater than 0 (UKU scale intensity score >0 signifies the presence of the given adverse reaction) will be compared between the groups for all 48 adverse effect monitored with UKU scale at two time points: 4 weeks after the enrolment (V1) and 8 weeks after the enrolment (V2). Due to large number of comparisons, significance measures will be adjusted using False Discovery Rate (FDR) correction. Proportion of individuals in two test groups affected with the given adverse reaction will be compared using binary logistic regression analysis separately for visit V1 and visit V2 as follows:

1. Dependent variable: Frequency of the individuals affected with the given adverse drug reaction measured by UKU scale

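### UKU, a primary outcome, has no scheduled V0 rating and no baseline term, so the V1 and V2 group comparisons may mix pre-treatment symptoms with drug effects

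*Combined protocol and SAP*

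**What the plan says.** The Primary outcomes section of the SAP introduces UKU with "Other primary outcome we will use to quantify changes in clinical outcomes between test groups will be severity of the treatment side effects". The 48 item scores "will be measured at weeks 4 (V1) and 8 (V2) after the initiation of the escitalopram therapy"; V0 is not listed.

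Two analyses are planned for each item, both with FDR correction:

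- A mixed ANCOVA on the item score, with the group-by-visit interaction as the positive outcome. Its covariate list starts "Covariables: Age, Sex (Male=0, Female=1), Smoking status (0=Non-smoker, 1=Smoker), Alcohol consumption (0=No, 1=Yes), Coffee consumption (0=No, 1=Yes" and goes on to psychoactive substance use, metabolic syndrome, creatinine clearance and AST/ALT ratio.
- As an alternative, "binary logistic regression analysis separately for visit V1 and visit V2", with test group as the factor of interest. Its list starts "Covariables: Test group (Personalized vs Standard dosing), Age, Sex (Male=0, Female=1), Smoking status (0=Non-smoker, 1=Smoker" and has the same remaining terms. Here a "UKU scale intensity score >0 signifies the presence of the given adverse reaction".

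Neither list contains a baseline UKU score or baseline HAM-D. Under Hypotheses, item 2 states that participants outside the therapeutic window "will experience reduced efficacy and more severe side effects of escitalopram therapy before dose personalization (at V1"). The Test groups section allocates participants by their week-2 escitalopram concentration.

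Other outcomes are handled differently. HAM-D (Primary outcomes), and HAM-A, serum cortisol and QT interval (Other outcome measures/observations), are all measured at baseline and adjusted for it.

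**The concern.** Without a pre-treatment rating, a score above 0 at V1 can mean a reaction to escitalopram or a complaint the patient already had. The documents give the rater and the analyst no rule for telling these apart.

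Randomisation would balance pre-treatment symptoms on average. Here the groups are defined by drug level, and the Secondary outcomes section says exposure may depend on body weight, liver and kidney function and CYP2C19 genotype. The groups may therefore differ in patient characteristics, and no UKU model adjusts for baseline severity or body weight. Nothing planned would show whether symptoms were balanced before treatment.

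At stake is the side-effect half of hypothesis 2, which attributes a V1 difference to escitalopram, and both per-visit logistic comparisons. The V2 comparison also bears on the claim in hypothesis 3 that the groups end up comparable.

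**Working it through.** The documents give no sample size, effect size or power for UKU, so there is no planned figure to reproduce. Group sizes, prevalences and variances below are assumptions. Equal groups are reasonable because the Secondary outcomes section expects about 40% below and 10% above the window, so about 50% in each group. Covariates and FDR are not modelled.

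1. **V1 test of one item when no reaction is drug-caused.** Let p1 and p2 be the proportions with a pre-existing symptom, m their mean and n the number per group. The chance of a significant result in the direction of the imbalance (two-sided 0.05) is Φ{(|p1 − p2| − 1.96·√[2m(1 − m)/n]) / √[(p1(1 − p1) + p2(1 − p2))/n]}. For 40% versus 50%:
   - n = 30: (0.1 − 1.96 × 0.1285)/0.1278 = −1.19, giving 12%.
   - n = 50: (0.1 − 1.96 × 0.0995)/0.0990 = −0.96, giving 17%.
   - n = 100: (0.1 − 1.96 × 0.0704)/0.0700 = −0.54, giving 29%.

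   For 40% versus 45% the same formula gives 6%, 7% and 11%; for 40% versus 60% it gives 34%, 52% and 81%. With equal prevalence the two-sided rate is 5%.

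2. **Dilution when baselines are equal.** If a proportion b has the symptom beforehand, it persists and is scored, and a proportion r of the rest develop it on drug, the observed proportion is b + (1 − b)r. With b = 0.3 and r = 0.2 this is 0.3 + 0.7 × 0.2 = 0.44, of which 0.3/0.44 = 68% is pre-existing. Over b = 10% to 50% and r = 10% to 30% the share runs from 27% to 91%. With b = 0.3, true incidences of 20% and 10% appear as 44% and 37%, so a 10-point difference shrinks to 7 points.

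3. **Per-visit contrast versus interaction.** Take a continuous score with person-level SD 0.8 and residual SD 0.6 (total SD 1), a pre-existing group difference of 0.3 SD, no drug effect, and 4,000 simulated trials per setting.
   - V1 contrast: significant in 33% of trials (50 per group) and 57% (100 per group).
   - Group-by-visit interaction with a constant offset: about 5% at both sizes, because the offset cancels in V2 − V1.
   - Interaction when pre-existing symptoms halve from V1 to V2: 13% and 20%. As an arithmetic check, the spurious difference in change is 0.5 × 0.3 = 0.15 and the variance of change is 0.25 × 0.64 + 2 × 0.36 = 0.88. For n = 50, 0.15/√(2 × 0.88/50) = 0.80 and Φ(0.80 − 1.96) = 12%, in line with the simulation.

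**The case against.** The strongest reply is that the success criterion for the UKU mixed ANCOVA is the group-by-visit interaction, which removes any stable difference between groups. That stands: the interaction fails only if groups differ at baseline and those symptoms also remit between V1 and V2. It does not protect hypothesis 2 at V1 or the per-visit logistic models, even though the latter are offered as an alternative.

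A reader might infer that every pre-existing complaint will be recorded as a side effect. The documents do not show this. UKU is clinician-reported and described as scoring adverse reactions, and the rating instructions are not in the documents, so raters may exclude earlier symptoms. What can be said is that no such rule is stated.

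A reader might also infer that the groups do differ before treatment. That is possible but not shown; the UKU models already adjust for age, sex, kidney function, AST/ALT ratio and metabolic syndrome, among others.

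The V0 visit lists clinical questionnaires without naming them, so UKU could be among them in practice. Even so, the SAP schedules it only at V1 and V2, and no model would use a V0 value.

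Last, it is tempting to state a power gain from baseline adjustment. The documents give no sample size or effect size, and a calculation for a continuous score at 0.05 would not describe logistic tests of 48 items under FDR.

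**Conclusion.** The gap is real: a primary outcome has no scheduled pre-treatment rating, no baseline term and no stated attribution rule, while HAM-D, HAM-A, cortisol and QT are baseline-adjusted. As planned, the V1 side-effect comparison and the V1 and V2 logistic models cannot separate drug effect from prior state.

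The size of any bias depends on imbalance that the documents neither show nor exclude. With a 10-point difference in pre-existing prevalence, the assumed cases in step 1 give false-positive rates of 12% to 29% for a single item before FDR. With no imbalance the rate stays at 5% and the harm is dilution and lost precision. FDR correction makes each test stricter, but it guards against chance findings, not against a real pre-treatment difference. The interaction is sound against a stable offset. The change is worth making, but the point does not show that the UKU results would be wrong.

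**What to change.** - In the standard course, rate UKU at V0 with the other clinical questionnaires, and state whether symptoms that pre-date treatment are to be scored.
- Add each item's V0 score as a covariate in its V1 and V2 logistic models.
- In the mixed ANCOVA, add the V0 score together with a baseline-by-visit term. As a main effect alone, with complete data, it leaves the interaction estimate unchanged.
- Alternative-course patients are already on escitalopram at V0, so their score is not a pre-treatment baseline, and adjusting for it could remove part of the drug effect. Run the baseline-adjusted UKU analysis in standard-course patients, and report the analysis of all patients without UKU baseline adjustment alongside it.
- Where V0 has already passed, add baseline HAM-D, which is already collected, as a covariate, and describe V1 results as symptoms present, not as drug effects. HAM-D is only a proxy, and in the alternative course it too is measured on drug.

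The cost is one 48-item clinician rating per patient at V0 and added baseline terms in 48 mixed models and 2 × 48 = 96 logistic models. The logistic models already carry test group and nine other covariates, so estimates for rare items may be unstable.

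### The UKU primary outcome has two analyses on different contrasts, each with its own success rule, and the SAP does not say which one decides

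*Combined protocol and SAP*

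**What the plan says.** All of this stands in the Statistical Analysis Plan under Primary outcomes, in the part on the UKU scale.

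- **Status.** "Other primary outcome we will use to quantify changes in clinical outcomes between test groups will be severity of the treatment side effects".
- **First analysis.** "Absolute values of all 48 Adverse reaction scores will be compared between test groups and between two time points", by mixed ANCOVA, one model per item. Its success rule is "Positive outcome: interaction between group and visit is significant", at α = 0.05.
- **Second analysis.** It opens with "Alternatively, proportions of patients with intensity score greater than 0". The proportions affected "will be compared using binary logistic regression analysis separately for visit V1 and visit V2 as follows". Its success rule is "Positive outcome: Test group is a significant factor", also at α = 0.05.
- **Multiplicity.** Each of the two descriptions has one sentence saying that an FDR correction will be used. The FDR method and the set of p-values it covers are not given.

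The SAP does not say when the second analysis replaces the first, whether it is supportive, which visit's logistic result counts, or how many of the 48 items must be significant.

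The Hypotheses section gives the clinical reading. Hypothesis 2 expects worse side effects in the out-of-window group at V1, before personalization. Hypothesis 3 expects that group to improve from V1 to V2 and to be comparable with the standard-dose group at V2.

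**The concern.** Two success rules stand for one primary outcome, and following the plan as written allows either of them to declare a positive result. This has two consequences.

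The first is interpretive. The interaction asks whether the group difference changed between visits. The logistic tests ask whether a difference exists at one visit. They can disagree, and two of the possible logistic positives would not support personalization at all.

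The second is the error rate. An FDR correction controls error within the set of p-values it is applied to. It does not cover the freedom to take a positive from one set or another. The 0.05 attached to each rule therefore does not describe the chance of a positive UKU finding by one route or the other.

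**Working it through.** **1. What each rule responds to.** Let d1 and d2 be the group differences for one item at V1 and V2, on a common scale. The interaction is d2 − d1. The logistic tests address d1 and d2 separately.

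| True pattern | Interaction (d2 − d1) | V1 test | V2 test |
|---|---|---|---|
| Same difference at both visits, d1 = d2 ≠ 0 | zero | non-zero | non-zero |
| Difference at V1 that disappears, d2 = 0 (as in hypotheses 2 and 3) | −d1 | non-zero | zero |
| Difference only at V2, d1 = 0 | d2 | zero | non-zero |
| Reversal, d2 = −d1 | −2·d1 | non-zero | non-zero, opposite sign |

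The table shows which true contrasts are non-zero. The documents give no sample size, so it says nothing about power. In the first row the logistic rule can be met although nothing changed after dose adjustment. In the third row a V2 difference meets the logistic rule while contradicting the comparability that hypothesis 3 expects. The V1 column is measured before any dose change, in groups formed by plasma level.

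**2. Inputs for the error rate.** From the SAP: 48 items; 48 interaction tests; 48 × 2 = 96 logistic tests; 48 + 96 = 144 in all; α = 0.05 for each rule. Assumed: two-sided tests, Benjamini-Hochberg, a global null, and success if any one item is significant after correction.

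**3. One analysis.** Under a global null with independent tests, Benjamini-Hochberg at 0.05 gives at least one rejection in 5% of trials, which matches the plan's stated level.

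**4. Reference values if families were independent.**
- Two families (interactions; 96 logistic tests under one FDR): 1 − 0.95² = 0.0975.
- Three families (interactions; V1 logistic; V2 logistic): 1 − 0.95³ = 0.1426.

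**5. Allowing for dependence.** The families share patients and items. I simulated 40,000 null trials per setting with z-statistics for 48 items at V1 and V2. The interaction z was (z2 − z1)/√(2(1 − ρ)), where ρ is the visit correlation, set to 0.3, 0.5 or 0.7. Ranges are over ρ.

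| Item correlation (assumed) | Interactions alone | Either of two families | Any of three families | One FDR over 144 |
|---|---|---|---|---|
| 0 | 5.0–5.1% | 9.3–9.4% | 13.4–13.5% | 4.7–4.9% |
| 0.3 | 4.4–4.5% | 8.2–8.5% | 11.7–12.1% | 4.5–4.6% |
| 0.5 | 3.5–3.7% | 6.6–6.9% | 9.3–9.4% | 3.7–3.8% |

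**6. Patient-level check.** The z-level model treats severity and presence as one measure. A second simulation drew 0–3 scores per patient and derived presence as a score above 0. It used 3,000 trials per setting, an assumed 100 or 200 patients split 1:1, assumed item prevalence of 15–50%, item correlation 0 or 0.3, and no covariates. Simple two-group tests stood in for the ANCOVA and logistic models. Either of two families gave 6.8–9.0%, and any of three gave 10.6–13.1%.

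**The case against.** The strongest reply is that both UKU analyses are fully written out in advance, with variables, covariates and an FDR correction. The primary outcome is named as severity, and only the first analysis uses severity scores. On this view the second is another way to express the same result, and all that is missing is one ranking sentence. Much of this is fair. A reader might infer that the sponsor means to choose the analysis after seeing results, but nothing in the SAP says so. What stands is that each analysis carries its own success rule, so running both still leaves two unranked routes to a positive.

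A reader might also take about 14% as the plan's false-positive rate. The documents do not support that. In the logistic description the FDR sentence follows a reference to all 48 items at two time points, and the word for separate handling belongs to the regressions. One FDR over 96 p-values is at least as natural a reading, and it gives the lower range. The any-item success rule is also not in the plan, whose rules can be read item by item. The global null is a device too: hypothesis 2 expects a real V1 difference, so a V1 rejection may be true. The objection to counting it is then relevance, not type I error.

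Finally, a reader might see the HAM-D analyses as a better-ordered model because they are conditioned on assumptions. They are not: each is conditioned on its own assumptions, and neither is linked to the other.

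**Conclusion.** The point holds as a missing ranking between two analyses of a primary outcome that test different contrasts. That conclusion rests on the text alone and needs no simulation. The inflation is real but moderate. It is about 7–9% if the presence tests share one FDR and about 9–14% if FDR is applied per visit, against about 4–5% for one named analysis. These figures depend on a global null, Benjamini-Hochberg at 0.05 per family, success on any one item by either route, and the assumed item and visit correlations. The plan settles neither the FDR family nor the number of items needed, so neither range can be called the trial's actual error rate.

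**What to change.** Replace the linking word with a ranking, for example:

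*The severity group-by-visit family (48 tests, one FDR) decides the UKU outcome for hypothesis 3. The presence/absence contrast at V1 addresses hypothesis 2 and is not evidence for personalization. The presence/absence contrast at V2 is supportive and carries no positive-outcome rule. One FDR correction covers all 96 presence/absence p-values.*

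The SAP should also name the FDR method and state how many items must be significant for the outcome to count as positive. Assigning V1 to hypothesis 2 matters, because demoting the presence models altogether would leave that hypothesis without a direct UKU success rule.

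If the sponsor wants either analysis to be able to declare success, apply one FDR over all 144 p-values. Under the global null this gives about 4–5%. The ranking is preferable because pooling does not resolve the difference in contrasts.

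**Cost.** The change is to SAP wording, with no new data, visits or models. Under the ranking, presence/absence cannot on its own declare success for personalization. Under pooling, the threshold is stricter: for a single isolated item the Benjamini-Hochberg cut-off falls from 0.05/48 = 0.00104 to 0.05/144 = 0.00035, and the gap narrows when several items are significant together.
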